# Appendix 9. Protocol Amendment I8F-MC-GPHH(f) Summary - Effect of Tirzepatide on Energy Intake and Appetite- and Reward-Related Brain Areas in Overweight/Obese Subjects: A Placebo-Controlled 6-Week Study with Functional MRI

#### **Overview**

Protocol I8F-MC-GPHH, Effect of Tirzepatide on Energy Intake and Appetite- and Reward-Related Brain Areas in Overweight/Obese Subjects: A Placebo-Controlled 6-Week Study with Functional MRI, has been amended. The new protocol is indicated by Amendment (f) and will be used to conduct the study in place of any preceding version of the protocol.

This amendment is considered a nonsubstantial protocol amendment.

The overall changes and rationale for the changes made to this protocol are as follows:

- Appendix 5 was updated to include language on
  - o the types of scanners on which MRI scanning will occur to specify the different scanners used across the different study sites and,
  - the hand squeezing task following the food image task to evaluate inter-scanner variability across the different scanners. The hand squeezing task produces consistent patterns of motor cortex activation in the brain, independent of scanner type.
    - The hand squeezing task will be used to ensure that the fMRI data from all sites can be analyzed collectively at the end of the study.
  - The description of preprocessing of fMRI data was deleted because it will be performed by an external imaging laboratory services provider.

# **Revised Protocol Sections**

**Note:** All deletions have been identified by strikethroughs.

All additions have been identified by the use of underscore.

#### **Appendix 5**

#### 5.2 Magnetic Resonance Imaging

Functional neuroimaging, in the forms of BOLD fMRI will be used to assess brain response patterns to food and non-food images. The MRI scanning will occur on different scanners such as a 3T General Electric Discovery 750W with 32-channel head coil, a 3T General Electric Discovery 750 with 32-channel head coil, a 3T Siemens Prisma with a 64-channel head coil, or a 3T Philips Achieva with a 32-channel head coil. Functional neuroimaging session will be conducted after participants fast overnight for at least 8 hours (ten Kulve et al. 2016).

Subjects will be required to complete the food image task during the BOLD fMRI scan. The food image task was developed using images from the Food-pic database (Blechert et al. 2014). Briefly, 90 food images across sweet and savory tastes, high- and low-energy density, and varied macronutrient composition, were included along with 15 images of non-food objects (e.g. everyday household objects). This results in 105 images in total.

For the purposes of evaluating inter-scanner variability to ensure that the fMRI data from all sites can be analyzed collectively at the end of the study, subjects will be required to complete a bilateral hand squeeze motor task during the BOLD fMRI scan, consisting of 4 blocks after the food image task. Each block will consist of 30 seconds of bilateral hand squeezing followed by 30 seconds of rest (around 3 minutes total run time).

#### **BOLD fMRI Data Processing**

The BOLD fMRI acquisition parameters include repetition time of 3000 ms, echo time of 30 ms, flip angle of 90°, slice thickness of 3.5 mm, and 64×64 image matrix.

As in prior work (King et al. 2018), a T1-weighted magnetization-prepared 180° radio-frequency pulses and rapid gradient-echo (MP RAGE) will be collected as an anatomical reference for functional data.

Preprocessing of fMRI data will be done by an external imaging laboratory services provider. in SPM8 includes slice-timing correction, head-motion correction, smoothing, and warping to a standard coordinate frame. Time points with head rotation greater than 2° or translation greater than 2 mm will be removed. Data will be entered into a first-level voxel-wise analysis with each trial modeled as a boxcar function that covers the period of time when the large image is viewed. The boxcar function is convolved with the canonical hemodynamic response function. Functional scans will be analyzed in the context of the general linear model.

For the hand squeezing fMRI task, BOLD contrasts of hand squeezing versus resting within bilateral somatomotor ROIs will be calculated. For the food image fMRI task, hHighly palatable food (HF-HS, HF-HCCHO), not highly palatable foods (low fat-low carbohydrate-high proteinLF-LCCHO-HP), and non-food object blocks will be modeled. To assess brain activation related to viewing food pictures, the contrast between highly palatable foods and non-food objects will be computed. Additionally, the contrast between highly palatable foods and not highly palatable foods as well as the contrast between not highly palatable foods and non-food objects may be computed. Contrasts between each specific food category and non-food objects

may also be computed if deemed necessary. Average BOLD contrast in each of 9 areas associated to brain reward will be reported (insula, medial frontal gyrus, superior temporal gyrus, precentral gyrus, cingulate gyrus, hippocampus, putamen, orbitofrontal cortex, and ventral striatum).

### 3. List of Abbreviations

Term	Definition
ADA	anti-drug antibody
BIS	Barratt Impulsiveness Scale
BMI	body mass index
BOLD fMRI	blood-oxygenation-level-dependent functional magnetic resonance imaging
AE	adverse event
AESI	adverse event of special interest
CI	confidence interval
COVID-19	coronavirus disease 2019
ECG	electrocardiogram
FCI	Food Craving Inventory
FCQ-S	Food Craving Questionnaire-State
GIP	glucose-dependent insulinotropic polypeptide
GLP-1	glucagon-like peptide 1
IPD	important protocol deviation
Lilly	Eli Lilly and Company
LSM	least squares means
MedDRA	Medical Dictionary for Regulatory Activities
MMRM	mixed effects model of repeated measures
MRI	magnetic resonance imaging
PD	pharmacodynamic(s)
PK	pharmacokinetic(s)
PT	Preferred Term
PYY	peptide YY
QD	once daily
QL	quantification limit

Term	Definition
QW	once weekly
ROI	region of interest
SAE	serious adverse event
SAP	statistical analysis plan
SOC	System Organ Class
TE-ADA(+)	treatment-emergent anti-drug antibody (positive)
TEAE	treatment-emergent adverse event
TFEQ	Three-Factor Eating Questionnaire
VAS	visual analog scale

## 4. Revision History

Statistical analysis plan version 1 was approved on 25 June 2020 prior to the first patient visit.

Statistical analysis plan version 2 was approved on 09 June 2022 prior to database lock.

The major revisions in version 2 include

- modified study procedure and schedule of activities based on Protocol (f)
- updated sample size to approximately 111 subjects (37 subjects per treatment arm) planned to be randomly assigned, and
- reorganized and rephrased the PD analyses section.

Statistical analysis plan version 3 was approved prior to database lock.

Major revisions in version 3 include

- Change of specification of the BOLD fMRI analysis variables. Contrasts between conditions are defined as the mean difference as opposed to mean percent difference. This is because dividing by the non-food contrast was causing falsely large numbers in scans where the subject had low activation to non-food objects (that is, division by number close to 0).

## 5. Study Objectives

Table GPHH.5.1 shows the objectives and endpoints of the study.

**Table GPHH.5.1. Objectives and Endpoints**

Objectives	Endpoints

Primary
 
To compare the effect of 5-mg tirzepatide versus placebo, at Week 3, on energy intake in a clinical setting
	
 
Change from baseline in energy intake (kcal) as assessed by ad-libitum food-intake test
 

Secondary
 
To compare the effect of 5-mg tirzepatide versus placebo, at Week 3 on
 
 
Parameters of central reward and appetite circuits in the fasting states using BOLD fMRI
 
Parameters of behavioral appetite assessments
 
	
 
Change from baseline in BOLD fMRI activation to images of highly palatable food (high fat-high sugar and high fat-high carbohydrate) during the fasting state in the brain reward areas (insula, medial frontal gyrus, superior temporal gyrus, precentral gyrus, and cingulate gyrus)
 
Change from baseline in fasting and postprandial appetite VAS, and fasting FCI, FCQ-S, Eating Inventory, and Power of Food Scale questionnaires
 

Exploratory
 
To compare the effect of 5- or 10-mg tirzepatide versus placebo at Week 3 and/or Week 6 on
 
 
Parameters of central reward and appetite circuits in the fasting state using BOLD fMRI (Week 6/10 mg)
 
Parameters of behavioral appetite assessments (Week 6/10 mg)
 
Energy intake in a clinical setting (Week 6/10 mg)
 
	
 
Change from baseline in BOLD fMRI activation to images of highly palatable food (high fat-high sugar and high fat-high carbohydrate) versus non-food objects during the fasting state in the brain reward areas (insula, medial frontal gyrus, superior temporal gyrus, precentral gyrus, cingulate gyrus)
 
Change from baseline in fasting and postprandial appetite VAS, and fasting FCI, FCQ-S, Eating Inventory, and Power of Food Scale questionnaires
 
Change from baseline in energy intake (kcal) as assessed by ad-libitum food-intake test
 

Objectives	Endpoints

 
Parameters of central reward and appetite circuits in the fasting state using BOLD fMRI (Week 3/5 mg and Week 6/10 mg)
 
Impulsivity (Week 3/5 mg and Week 6/10 mg)
 
Appetite and metabolism regulating hormones (Week 3/5 mg and Week 6/10 mg)
 
	
 
Change from baseline in BOLD fMRI activation to images of highly palatable food (high fat-high sugar and high fat-high carbohydrate) during fasting state in the hippocampus, putamen, orbitofrontal cortex, and ventral striatum brain regions
 
Change from baseline in BIS questionnaire
 
Change from baseline in ghrelin, glucagon, glucose, and triglycerides (fasting), insulin (fasting and postprandial), and amylin, GIP, GLP-1, leptin, pancreatic polypeptide, and PYY (postprandial)
 

To compare the effect of 5- and 10-mg tirzepatide versus liraglutide and tirzepatide versus placebo at Week 3 and/or Week 6 on
 
 
Energy intake in a clinical setting (Week 3/5 mg and Week 6/10 mg)
 
Parameters of behavioral appetite assessments (Week 3/5 mg and Week 6/10 mg)
 
Parameters of central reward and appetite circuits in the fasting states using BOLD fMRI (Week 3/5 mg and Week 6/10 mg)
 
Appetite and metabolism regulating hormones (Week 3/5 mg and Week 6/10 mg)
 
	
 
Changes from baseline in energy intake (kcal) as assessed by ad-libitum food-intake test
 
Change from baseline in fasting and postprandial appetite VAS, and the fasting FCI, FCQ-S, Eating Inventory, and Power of Food Scale questionnaires
 
Change from baseline in BOLD fMRI activation to images of highly palatable food (high fat-high sugar and high fat-high carbohydrate) during the fasting state in the brain reward areas [insula, medial frontal gyrus, superior temporal gyrus, precentral gyrus, cingulate gyrus, hippocampus, putamen, orbitofrontal cortex, and ventral striatum])
 
Change from baseline in ghrelin, glucagon, glucose, and triglycerides (fasting), insulin (fasting and postprandial), and amylin, GIP, GLP-1, leptin, pancreatic polypeptide, and PYY (postprandial)
 

Objectives	Endpoints
To assess the safety and tolerability of tirzepatide.	

• Adverse events

• Safety laboratory parameters

• Frequency of treatment-emergent anti-tirzepatide antibodies

Abbreviations: BIS = Barratt Impulsiveness Scale; BOLD = blood-oxygenation-level-dependent; FCI = Food Craving Inventory; FCQ-S = Food Craving Questionnaire-State; fMRI = functional MRI; GIP = glucose-dependent insulinotropic polypeptide; GLP-1 = glucagon-like peptide 1; MRI = magnetic resonance imaging; PYY = peptide YY; VAS = visual analog scale.

## 6. Study Design

### 6.1. Study Design and Treatment

This is a Phase 1, multicenter, randomized, partially blinded, placebo-controlled, parallel-arm study, with a positive control, liraglutide, in overweight/obese subjects. The primary objective of this study is to compare the effect of tirzepatide versus placebo on energy intake, as assessed by an ad-libitum food-intake test, at Week 3 of treatment at a therapeutic dose of 5 mg. Secondary objectives will compare these treatment groups for parameters of central reward, appetite circuits, and behavioral appetite assessments at Week 3.

Additional exploratory objectives will assess the effect of 10-mg tirzepatide versus placebo on energy intake, parameters of central reward and appetite, and behavioral appetite assessments at Week 6. Further exploratory analysis will assess the effect of tirzepatide versus liraglutide and liraglutide versus placebo on energy intake, parameters of central reward and appetite signaling, and behavioral appetite assessments at Week 3 and/or 6.

The study will consist of the following periods: approximately 5-week screening period, 5-day lead-in period, 6-week treatment period, and a 4-week safety follow-up period. Subjects will be randomized in a 1:1:1 ratio to placebo, tirzepatide, or liraglutide. Investigators and subjects will be blinded to tirzepatide and placebo treatment; however, liraglutide treatment will be open label, so the study is considered partially blinded. The randomization will be stratified by baseline BMI (27 to less than 30 kg/m^2, 30 to less than 35 kg/m^2, and 35 to 50 kg/m^2).

Tirzepatide QW dosing will start at 5 mg for 3 weeks followed by a dose escalation to 10 mg for 3 weeks. Subjects will return to the clinical research unit each week for the QW administration of tirzepatide or placebo.

[figure not shown]
Liraglutide QD dosing will start at 0.6 mg for 1 week followed by weekly, step-wise dose escalations to 1.2, 1.8, and 2.4 mg, until a 3-mg QD dose is reached. The 3-mg dose of liraglutide will be maintained for 10 days. Subjects will self-administer liraglutide at home in the evening.

Figure GPHH.6.1 illustrates the study design.

## 6.2. Determination of Sample Size

Up to 111 subjects (37 subjects per treatment arm) are planned to be randomized so that approximately 93 subjects (31 subjects per treatment arm) complete the study, assuming a 15% discontinuation rate.

These 111 subjects will be randomized to tirzepatide, liraglutide, or placebo in a 1:1:1 ratio. The estimated variability (standard deviation) of the change in energy intake from baseline is 289 kcal on the results from GPGC and blinded data from study GPGT Study I8F-MC-based based on an expected treatment difference of 212 kcal, this provides at least 80% power for the comparison of tirzepatide versus placebo based on a 2-sample t-test using a 2-sided test at an  $\alpha$  level of 0.05.

Abbreviations: BOLD = blood-oxygenation-level-dependent; fMRI = functional MRI; MRI = magnetic resonance imaging; QD = once daily; QW = once weekly.

Figure GPHH.6.1.

Illustration of study design for Protocol I8F-MC-GPHH.

## 7. A Priori Statistical Methods

### 7.1. Populations for Analyses

For the purpose of analysis, [Table GPHH.7.1](#) defines 3 analysis sets.

**Table GPHH.7.1. Analysis Populations and Analysis Datasets**

Population/Data Set	Description
Randomized population	All subjects who are randomly assigned to a treatment arm
Safety population	All randomized subjects who receive at least 1 dose of the randomly assigned IP, regardless of whether they completed all protocol requirements
Pharmacodynamic analysis set	All randomized subjects who receive at least 1 dose of the randomly assigned IP and have evaluable data

Abbreviations: IP = investigational product; MRI = magnetic resonance imaging; PD = pharmacodynamic.

Note: Protocol deviations will be considered for their severity/impact and taken into consideration if subjects should be excluded from PD analysis set for MRI data-related analyses.

### 7.2. General Considerations

Statistical analysis of this study will be the responsibility of Lilly or its designee. Any change to the statistical methods described in the protocol will require a protocol amendment only if it changes a principal feature of the protocol. Any other change to the statistical analyses and the justification for the change will be documented in this SAP.

Unless otherwise specified, safety analyses will be conducted on the safety population ([Table GPHH.7.1](#)), and PD analyses will be conducted on the PD analysis set ([Table GPHH.7.1](#)).

Unless otherwise specified, the baseline values used for analyses will be the last scheduled, nonmissing value obtained for each subject before first dose.

Unless otherwise noted, all tests of treatment effects will be conducted at a 2-sided  $\alpha$  level of 0.05, and the CI will be calculated at 95%, 2-sided.

### 7.3. Study Participant Characteristics

Subject baseline demographic and clinical characteristics will be summarized for the randomized population by study treatment (including overall). Specifically, the following baseline parameters will be included in (but not limited to) the summary report:

- age (years)
- gender (male and female)
- race
- ethnicity (Hispanic and Non-Hispanic)
- body weight (kg)
- height (cm)
- BMI ( $\text{kg}/\text{m}^2$ )
- BMI (27 to less than 30, 30 to less than 35, and 35 to 50  $\text{kg}/\text{m}^2$ ), and

- waist circumference (cm).

## 7.4. Study Participant Disposition

A listing and a summary of subject disposition for the randomized population (that is, subjects who have been assigned to a treatment) by actual study treatment will be provided.

A listing of patients who discontinue from the study for any reason for the randomized population will be provided, and the extent of their participation in the study will be reported. The reason for their discontinuation from study will be reported. The listing will also include age, sex, race, treatment, and study period.

## 7.5. Concomitant Therapy

Concomitant medications will be listed and summarized by treatment and World Health Organization Drug Dictionary Medication Class and PT for the safety population. In addition, concomitant medication taken by 10 or more subjects, regardless of treatment, will also be summarized.

## 7.6. Treatment Exposure and Compliance

### 7.6.1. Treatment Exposure

A listing of enrolled subjects who had inadvertently received the incorrect study treatment anytime during the study will be provided, if applicable.

The duration of exposure to study treatment (tirzepatide, liraglutide, or placebo) is defined as

$$\text{date of last dose of study treatment} - \text{date of first dose of study treatment} + 7 \text{ days}$$

The duration of exposure to study treatment will be summarized by treatment using the safety population.

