### 7. Treatment

#### 7.1. Treatment Administered

Subjects will receive tirzepatide or placebo administered SC QW for 6 doses or liraglutide administered SC QD for 38 days. Table GPHH.2 shows the treatment regimens.

Table GPHH.2. Study Treatments and Dose Escalation

Dosing Schemes						
Treatment	Week 1	Week 2	Week 3	Week 4	Week 5	Week 6
Tirzepatide	$1 \times 5$ -mg PFS	$1 \times 5$ -mg PFS	$1 \times 5$ -mg PFS	1 × 10-mg	1 × 10-mg	1 × 10-mg
	(Day 1)	(Day 8)	(Day 15)	PFS (Day 22)	PFS (Day 29)	PFS (Day 36)
Placebo	$1 \times PFS$	$1 \times PFS$	$1 \times PFS$	$1 \times PFS$	$1 \times PFS$	$1 \times PFS$
	(Day 1)	(Day 8)	(Day 15)	(Day 22)	(Day 29)	(Day 36)
Liraglutide	$0.6~\mathrm{mg~QD}$	1.2 mg QD	1.8 mg QD	2.4 mg QD	3 mg QD	3 mg QD
	(Days 1-7)	(Days 8-14)	(Days 15-21)	(Days 22-28)	(Days 29-35)	(Days 36-38)

Abbreviations: PFS = prefilled syringe; QD = once daily.

Tirzepatide or placebo will be administered QW at the CRU in a blinded fashion.

Liraglutide will be administered QD in an open-label manner and will be self-administered in the evening by the subject at home. Subjects will receive adequate training for liraglutide self-administration from site personnel.

All injections will be administered into the SC tissue of the abdominal wall. Injection sites will be alternated weekly for tirzepatide/placebo and daily for liraglutide, between 4 sites (right and left lower quadrants and right and left upper quadrants) of the abdominal wall.

Dosing will occur at approximately the same time of day in all groups and on the same day for the QW groups. The actual time of dosing will be recorded in the subject's electronic case report form (eCRF).

Whenever possible, IP administration at the CRU should be carried out by the same personnel. Additional details are provided in Section 7.3 (Blinding). The personnel who administer study drugs will be unblinded to liraglutide, but they will remain blinded to subjects receiving tirzepatide or placebo.

The investigator or designee is responsible for:

- explaining the correct use of the IP to the site personnel
- verifying that instructions are followed properly
- maintaining accurate records of IP dispensing and collection
- and returning all unused medication to Lilly or its designee at the end of the study

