### 7.6.2. Treatment Compliance

Percent compliance will be listed for each patient and summarized by treatment on the safety population. Percent compliance and treatment compliance will be summarized by treatment for each period and by treatment only.

Percent compliance will be calculated for each subject as

$$\frac{(\text{Number of injections administered [regardless of actual dose in mg administered]} \div \text{total number of injections expected to be administered}) \times 100}{}$$

Patients will be considered treatment compliant if taking 75% or more of their scheduled doses for the 6-week treatment period, considering early termination (specifically excluding the period after early termination).

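### The SAP's exposure formula adds 7 days in every arm, so a full 38-day course of once-daily liraglutide is reported as 44 days

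*SAP*

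**What the plan says.** SAP 7.6.1 names all three arms in one definition: "The duration of exposure to study treatment (tirzepatide, liraglutide, or placebo) is defined as" the date of the last dose minus the date of the first dose, plus 7 days. It then says how the result is used: "The duration of exposure to study treatment will be summarized by treatment using the safety population". There is no separate rule for the daily arm. SAP Section 9, which lists changes from the protocol's analyses, deals only with the BOLD contrast.

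The dosing schedules differ by arm. Protocol 7.1 says: "Subjects will receive tirzepatide or placebo administered SC QW for 6 doses or liraglutide administered SC QD for 38 days". SAP 6.1 gives the liraglutide schedule in two parts: "Liraglutide QD dosing will start at 0.6 mg for 1 week followed by weekly, step-wise dose escalations to 1.2, 1.8, and 2.4 mg", and then "The 3-mg dose of liraglutide will be maintained for 10 days". Table GPHH.2 in the protocol puts the last weekly dose on Day 36 and the last liraglutide dose on Day 38. SAP 6.1 gives the treatment period as 6 weeks.

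**The concern.** In a duration-of-exposure formula, the constant added to last minus first dose date usually credits the time that the last dose covers. For a weekly injection that is 7 days; for a daily injection it is 1 day. The SAP applies the weekly value to a daily drug.

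At stake is the by-treatment exposure table. It would show a liraglutide subject who followed the plan exactly as having 44 days of exposure, although that subject has 38 planned daily injections and a treatment period of 42 days. A reader comparing arms would see liraglutide with slightly longer exposure than the weekly arms and would not know that 6 of those days come from a weekly interval. Subjects who stop early are included, because the safety population requires only one dose (SAP Table GPHH.7.1), and for them the same 6 days are a larger share of the total.

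**Working it through.** **Inputs**

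- Formula: last dose date - first dose date + 7 days, all arms (SAP 7.6.1).
- Weekly arms: first dose Day 1, last dose Day 36, six doses (Protocol 7.1, Table GPHH.2).
- Liraglutide: first dose Day 1, last dose Day 38, once daily (Protocol 7.1, Table GPHH.2).
- Liraglutide schedule in the SAP: four weekly steps plus 10 days at the final step (SAP 6.1).

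**Step 1. Reproduce the planned liraglutide course.** From SAP 6.1: 4 × 7 + 10 = 38 days. From the day ranges in Table GPHH.2: 7 + 7 + 7 + 7 + 7 + 3 = 38 days. Protocol 7.1 prints 38 days. The SAP does not print the total, but its schedule gives the same one.

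**Step 2. Apply the SAP formula to full planned courses.**

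- Tirzepatide or placebo: 36 - 1 + 7 = 42 days, which is 6 doses × 7 days and equals the 6-week treatment period.
- Liraglutide: 38 - 1 + 7 = 44 days, which is 2 days longer than the treatment period.

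**Step 3. Credit one daily interval for liraglutide.** 38 - 1 + 1 = 38 days, which matches the planned course. The excess under the SAP formula is 7 - 1 = 6 days, or 6/38 = 15.8%.

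**Step 4. Earlier last doses.** The excess stays at 6 days whatever the stopping day. These cases are illustrations; the documents give no distribution of stopping times.

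| Last liraglutide dose | SAP formula (+7) | Daily interval (+1) | Excess |
|---|---|---|---|
| Day 38 | 44 | 38 | 6/38 = 15.8% |
| Day 28 | 34 | 28 | 6/28 = 21.4% |
| Day 21 | 27 | 21 | 6/21 = 28.6% |
| Day 14 | 20 | 14 | 6/14 = 42.9% |
| Day 7 | 13 | 7 | 6/7 = 85.7% |

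Because the excess is constant, the liraglutide mean and median both move up by 6 days and the standard deviation does not change.

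**Step 5. Between-arm comparison, full planned courses only.** Liraglutide minus weekly arm is 44 - 42 = +2 days under the SAP formula and 38 - 42 = -4 days with arm-specific intervals. The +2 is the difference in first-to-last-dose span: (38 - 1) - (36 - 1) = 37 - 35 = 2. A common added constant leaves that difference as it is.

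**Step 6. Where the duration is used.** Percent compliance in SAP 7.6.2 counts injections. The primary ANCOVA (SAP 7.9.2.1), the MMRM analyses (SAP 7.9.2.2) and the treatment-emergent adverse event summaries (SAP 7.10.2) do not use exposure time. Only the summary in SAP 7.6.1 is affected.

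**The case against.** The best reply is that SAP 7.6.1 defines a derived variable and does not miscalculate one. The SAP never says that the variable should equal the number of dosing days, and it never says that 7 stands for the weekly interval. A common 7-day tail after the last dose could be deliberate, and the 6-day excess exists only if one chooses to credit a single dosing interval. The study does count equally from the last dose elsewhere: the follow-up visits fall 23 and 28 days after the last dose in every arm (59 - 36 and 61 - 38; 64 - 36 and 66 - 38). The +2-day difference between arms is a true difference in dosing span. The formula is printed, so a reader can subtract 6 days, and no conclusion on efficacy or safety depends on it.

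Part of this stands. The meaning of the 7 is an inference, the reference rule is a convention, the sign of the between-arm difference depends on that convention, and the practical effect is small. What does not stand is the defense of the formula for the daily arm. The follow-up offsets concern visit timing, not time on treatment. The 7 gives exactly 42 days for six weekly doses and gives more than the treatment period for a daily course that ends on Day 38. If a common tail was meant, the SAP gives no reason for it, and a table labeled as duration of exposure would still credit 7 days to a single daily injection.

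**Conclusion.** The concern holds. Followed as written, SAP 7.6.1 reports 44 days for a 38-day liraglutide course and overstates every liraglutide subject's exposure by 6 days. This rests on one assumption: that exposure should extend one dosing interval past the last dose, 7 days for the weekly arms and 1 day for the daily arm. The weekly figures are sound under the same assumption. The point is minor, because it is confined to one descriptive summary. The 44-against-38 and between-arm figures apply to subjects dosed exactly on the planned first and last days; the 6-day excess applies to any liraglutide subject.

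**What to change.** In SAP 7.6.1, define duration of exposure separately by dosing frequency:

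- tirzepatide and placebo: last dose date - first dose date + 7 days;
- liraglutide: last dose date - first dose date + 1 day.

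If a common 7-day tail after the last dose is intended, state the reason in SAP 7.6.1 and also report the liraglutide duration with 1 day added, so that the table shows time on daily dosing.

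The change costs one line in the SAP and one programming condition. It needs no new data and alters no other analysis. The SAP already separates the arms where their schedules differ: Table GPHH.7.2 lists different follow-up days for liraglutide.
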